##### **Exclusion Criteria:**

- No active wound healing or skin breakdown issues.
- No history of poorly controlled autonomic dysreflexia.
- Medical contraindications for general anesthesia, craniotomy, or surgery.
- Diagnosis of acute myocardial infarction or cardiac arrest within previous 6 months.

- Participants with any type of destruction and/or damage to the motor cortex region as determined by MRI.
- Dementia
- Psychiatric disturbances
- Other implantable devices such as heart/brain pacemakers
- Participants who rely on ventilators
- Co-morbid conditions that would interfere with study activities or response to treatment, which may include:
  - Life expectancy < 3 years
  - Severe chronic pulmonary disease
  - Confirmed seizure disorder that requires continued clinical care
  - Local, systemic acute or chronic infectious illness
  - Life threatening cardiac arrhythmias
  - Severe collagen vascular disorder
- Kidney failure or other major organ system failures History of a neurological ablation procedure.
- Labeled contraindication for MRI.
- History of hemorrhagic stroke.
- History of HIV infection or ongoing chronic infection (such as tuberculosis).
- Pregnant or of child-bearing potential and are not taking acceptable methods of contraception.

Participation in another investigational device or medication trial

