#### **3.2.3 Phase III - Decoding and Stimulation**

Neural signals from the implant will be monitored and re-coded by the Neural Bridging System. Re-coding involves the process of decoding neural signals and then encoding the appropriate stimulation patterns for an intended movement. Decoding algorithms will decipher neural signals using pattern recognition methods to classify different movements imagined by the participant. The Battelle Neuromuscular stimulator will be setup and calibrated to evoke the imagined wrist and hand/finger movements. Encoding algorithms will use the calibration data and the decoded data to create the appropriate spatial and temporal stimulation patterns to evoke imagined movements.

Each subject will be asked to participate in test sessions, for up to 3 times a week for about 60 months. Each session will typically last less than 4 hours (including setup time). The first 30 minutes, approximately, will be needed for setup of the Blackrock and stimulator system. Once the stimulator is calibrated, the participant will be asked to imagine wrist and hand movements and the decoding algorithms will identify the desired movements. Once a select set of imagined movements have been identified, the stimulator system will apply the appropriate spatial stimulation patterns to the forearm to achieve motion in the paralyzed limb. This will give the patient voluntary control of the select movements in the paralyzed limb. Neurophysiological recordings and evaluations will also be conducted during these test sessions. Active stimulation time will be monitored to avoid fatigue. Trained study personnel will set up and perform the device during the study visits. At the conclusion of the study, the patients will have the cortical implant removed via a second procedure.

The participant(s) will receive haptic feedback above the level of their injury during motor tasks to enhance their motor performance. Haptic feedback simply provides a skin sensation (e.g. vibration), is well characterized in the literature (Shull & Damian, 2015), and is a well-studied and safe stimulus carrying no significant increase in risk. The apparatus will be electrically isolated from the participant. The participants currently receive electrical skin stimulation for feedback in the study. Haptic feedback is a non-electrical safer means of providing even more meaningful sensory information to enhance motor capability.

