During this phase of the study a virtual reality headset may be used to provide visualizations of imagined movements. If the virtual reality headset is not used, the virtual environment will be displayed on a screen. On occasion, the virtual reality headset may show the participant incongruent movements, that is, movements different from reality, to study the participant's sense of agency. This reanimation study offers a unique opportunity to study the neural mechanisms of motor awareness, such as sense of agency or movement intentions. Agency is the sense that we control the actions of our own body (Gallagher, 2000; Jeannerod, 2003) and is a fundamental aspect of the experience of self. In this study, normal efferent and afferent sensorimotor information is replaced by the reanimation system and visual feedback, respectively. Congruent and incongruent visual feedback presented via virtual reality may

provide important information about the fundamental mechanisms of self-awareness. The importance of showing both congruent (the VR representation looks the same as the intended movement) and incongruent (the VR representation shows different movement than the participant's intended movement, is important in understanding whether or not the participant is self-aware of the movements he is making with his paralyzed limb. This type of VR experiment is currently being done with the participant (i.e. showing congruent and incongruent movements), but on a flat screen which is a less immersive and less engaging environment. The addition of the device may remove some bias of the participant being able to see his limb, which is typically covered to some degree, but is never completely out of view.

Use of VR will advance our current “screen-limited” understanding of the reasons that influence ownership or control a person with tetraplegia may have over a hand or limb they cannot feel. It is anticipated that improving visualization and subjective feeling of movement during training will enhance training efficiency and make it easier for participants to move their limbs. We will explore whether brain-computer interface training using virtual reality decreases training time compared to standard (non-VR) training protocols.

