### **Transcranial magnetic stimulation (TMS)**

To complement the fMRI motor mapping of the motor cortex that is being used for pre-surgical implant location planning and post-explant evaluation of motor cortex plasticity, we will also include transcranial magnetic stimulation (TMS) pre-implant and post-explant to map the hand and arm area of the motor cortex. TMS is a non-invasive brain stimulation method that delivers a magnetic pulse through the surface of the skull to the motor cortex. This induces a depolarization of neurons in the corticospinal tract, which results in a twitch of peripheral limb muscles innervated by that brain region. This modality is commonly used clinically as an alternative to fMRI for pre-surgical motor mapping to assist in planning prior to brain surgery. It is used experimentally to investigate corticospinal tract plasticity associated with motor recovery, e.g., after stroke. Potential risks include seizures (2%, mostly among patients who were previously known to have seizures) and headache. Mapping of the hand/arm area with MRI-navigated TMS in patients with spinal cord injury serves 3 purposes: 1) it validates the cortical motor maps obtained through fMRI; 2) it distinguishes the sectors of cortical motor maps that are capable of controlling voluntary motion through the corticospinal tract in the spinal cord from areas that have been rendered mute from cord injury; and 3) it allows for quantification of plasticity, or change in sectors of motor maps that are capable of controlling voluntary motion through the corticospinal tract after stimulator explant.

We will perform TMS pre-implant (baseline, phase I) and post-explant (follow-up, phase IV).

We will deliver navigated TMS based on the patient's brain MRI scans to stereotactically identify and target near the "hand knob" of the primary motor cortex on the central sulcus.

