**Figure 4. Block diagram of the virtual reality headset used with the Neural Bridging System**

Risks Associated with the Oculus Rift Virtual Reality Device Alone:

- Seizures (1 in 4000 people)
- Electrical shock
- Repetitive stress injury such as muscle, joint, or skin pain
- Eye discomfort, eye muscle twitching, visual problems
- Dizziness
- Skin irritation

Risks associated with VR use will be mitigated by close patient monitoring, exclusion of patients with history of seizure or pacemaker, electrical isolation from the Neural Bridging System, and periodic device monitoring by the OSU Clinical Engineering Department. The VR device has

passed Clinical Engineering inspection to verify that no significant current is leaking from the electrical components of the device.

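### Section 4.5.1 counts on excluding people with a seizure history and people needing critical monitoring equipment, but 3.1.1 and 3.2.3 carry a weaker rule or none

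*Combined protocol and SAP*

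**What the plan says.** Section 4.5.1 states that the risk controls it identified were built into either the product or the trial protocol. For the VR headset, the controls are close monitoring, electrical isolation, periodic device checks and "exclusion of patients with history of seizure or pacemaker".

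The exclusion list in 3.1.1 names heart and brain pacemakers outright. Its only seizure item is "Confirmed seizure disorder that requires continued clinical care", one of several examples under the bullet "Co-morbid conditions that would interfere with study activities or response to treatment, which may include".

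Section 3.2.3 introduces the headset in Phase III: "During this phase of the study a virtual reality headset may be used to provide visualizations of imagined movements". It gives an alternative, "If the virtual reality headset is not used, the virtual environment will be displayed on a screen", but does not say who must use that alternative.

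The hazard table in 4.5.1 (without the VR device) lists six controls against electrical shock and burns. Two are stated as exclusions that the protocol already makes: people who need life-supporting equipment, and people who need critical health monitoring equipment.

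**The concern.** A hazard analysis that relies on an exclusion is only as good as the screening rule that carries it out. A coordinator screening from 3.1.1, or setting up a session from 3.2.3, would not meet the seizure-history rule that 4.5.1 relies on, and would find no rule on monitoring equipment. Someone whom the hazard analysis treats as excluded could then be enrolled or given the headset without anyone departing from those two sections. What is at stake is participant safety and the accuracy of the plan's account of its own controls. No sample size, error rate or efficacy estimate is affected.

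**Working it through.** There is no figure in the plan to reproduce. The check sets each control beside the text that should carry it out.

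1. **Seizure history at entry.** Section 4.5.1 refers to any history of seizure. The 3.1.1 item is narrower in two ways: there must be a confirmed disorder, and it must need continuing care. It also sits under a bullet limited to conditions that would interfere with the study. Take a person with one past seizure, or with a resolved disorder no longer under care. Under 4.5.1 that person is excluded. Under 3.1.1 the person is not named, and is excluded only if the history is judged to interfere. Under 3.2.3 the headset is allowed.

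2. **Seizure arising after entry.** The plan names two sources before Phase III. One is baseline transcranial magnetic stimulation: "Potential risks include seizures (2%, mostly among patients who were previously known to have seizures) and headache". The other is the implant surgery, where section 4.1 lists seizures as a risk. An entry criterion cannot catch either. Section 4.1.1 lets investigators end participation at the onset of epilepsy, but this is discretionary, a single seizure need not be epilepsy, and no rule on headset use follows.

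3. **Equipment.** Comparing the table's two exclusions with 3.1.1:
   - Life-supporting equipment: not named as such, but largely covered by the ventilator, implant, organ-failure, pulmonary and arrhythmia items.
   - Critical health monitoring equipment: not named. The same items, together with recent infarction or cardiac arrest and contraindications to anaesthesia or craniotomy, would remove some of these people.

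4. **Size.** Section 4.1 gives a VR seizure risk of about 1 in 4,000, that is 1/4,000 = 0.025%, for users in general. Excess risk from the seizure mismatch would be:

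   (number of affected participants) × (headset seizure risk given a seizure history − screen seizure risk given a seizure history)

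   The number affected lies between 0 and 5, since up to 5 people will be enrolled. Neither risk by seizure history is given, so the product cannot be computed. For the cost of a fix, each participant kept off the headset removes 1/5 = 20% of the largest possible headset sample.

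**The case against.** The strongest reply is that section 4.5.1 is itself part of the investigational plan, and the section on regulations and ethical conduct requires the study to follow that plan. Section 3.2.3 only permits the headset, so the 4.5.1 wording can be read as already barring anyone with a seizure history from VR, including a history acquired on study. This stands to a large extent. It reduces the seizure half of the point to two parts of one plan giving rules of different strength, with the weaker ones in the eligibility list and the VR procedure. It does not help with monitoring equipment, because there the table reports an exclusion that 3.1.1 does not contain.

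A reader might infer that people with a seizure history would be safer with the screen. The documents do not show this. Section 4.1 likens the VR seizure risk to that of watching television, and gives no risk by seizure history for either display.

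A reader might also infer that these hazards are left uncontrolled. They are not. Close monitoring and electrical isolation still apply to VR use. The monitoring-equipment exclusion is one of six controls in its row, alongside a design standard, current limiting on every channel and a fuse, and section 4.5.2 adds electrical isolation from mains power.

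**Conclusion.** The point holds as a minor internal inconsistency. One control (seizure history) is carried only in part by 3.1.1 and not at all by 3.2.3. Another (critical monitoring equipment) is said to be in the protocol but is not named in 3.1.1, although related items cover some of the same people.

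Confidence is high for the mismatch in wording. It does not extend to any effect on participants: no excess risk can be computed, and the weight each control carried in the risk scoring lies in hazard documents (D8208-022 and D8208-051) that are not part of this file. The conclusion assumes that staff screen and run sessions mainly from 3.1.1 and 3.2.3, which is usual but not stated. If they also apply 4.5.1 at each headset session, the seizure half becomes a missing cross-reference.

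**What to change.** - **Section 3.2.3:** after the sentence on the screen display, add that a participant with any history of seizure, including one that arises after enrolment, will not use the VR headset. This also reaches someone already in the study, whom a new entry criterion would miss. The plan implies there is one: "This type of VR experiment is currently being done with the participant".
- **Section 3.1.1:** add an exclusion for anyone who requires life-supporting or critical health monitoring equipment.
- **Section 4.5.1:** leave the VR mitigation wording as it is. If it is narrowed to headset use only, re-check the risk scoring in D8208-051. If the monitoring-equipment control is struck instead of being added to 3.1.1, re-check D8208-022.

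The reason for the headset rule is that it carries out a control the plan already claims. It does not rest on any shown benefit of the screen.

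The cost is a short amendment. An affected participant would keep the screen display but contribute no headset data to the comparison of VR with standard training, which the plan treats as exploratory.

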#### **4.5.2 Interaction between Devices**

The Neuroport device will collect neural signals as a subject imagines various movements, the data will be processed in real-time, and corresponding stimulation patterns will be sent to the Neuromuscular Stimulator. For example, a subject will imagine the flexion of their wrist and the stimulation patterns required to cause wrist flexion will be provided (after a short delay).

The Neuroport device will continuously monitor neural activity, passing the data to the re-coding algorithms running in Matlab (Natick, MA) on the PC. These algorithms will first decode the neural data (as was done in the BrainGate study), and then will provide the spatial and temporal stimulation patterns required to the subject to achieve the imagined movement. The spatial and temporal stimulation patterns for each subject will be different due to differences in anatomy, but will be determined during a ‘calibration’ session to map the various electrodes to the desired movements.

Once the neural activity resulting from an imagined movement is recognized and re-coded to determine the appropriate stimulation patterns, the stimulation pattern commands are sent to the Neuromuscular Stimulator via a USB connection (that is electrically isolated). The Neuromuscular Stimulator will then activate the appropriate electrodes in the NMES to evoke the desired movement. Furthermore, the Blackrock Neuroport device is electrically isolated from mains power to the patient. In addition, the Neuromuscular Stimulator is electrically isolated from mains power and earth ground and is compliant with the applicable patient and touch leakage currents in accordance with IEC60601-1:2005. Therefore, the two Neural Bridging subsystems that are in contact with the patient are electrically isolated and do not provide an unsafe current leakage path through the patient.

#### **4.5.3 Stimulation Parameters**

The stimulation parameters of the Neuromuscular Stimulator are as follows:

- Maximum peak current is 20mA with a maximum pulse width of 0.5ms.

- Maximum pulse frequency is 50 pulses per second.
- Nominal output voltage is  $200V \pm 10\%$  with maximum output of 300V.
- Maximum average current density is  $2 \text{ mA/cm}^2$  at the NMES electrode surface.
- Maximum average power density is  $0.25 \text{ W/cm}^2$  at the NMES electrode surface.

#### **4.5.4 Battelle Quality System**

Battelle Medical Products is an operational entity within Battelle in Columbus, Ohio. Medical Products' operations are guided by a set of operating budgets and goals that are defined and updated on an annual basis. As such, Battelle Medical Products is operationally accountable for all projects assigned to the group, administratively accomplished under its organization code(s), which identify Medical Products as the controlling entity for the contractual obligation with our customers.

All projects conducted within Battelle Medical Products fall under the Quality System (QS). The Battelle Medical Products QS is certified to ISO 13485:2003 and ISO 9001:2008, in addition to being compliant with the FDA's Quality System Regulation (21CFR Part 820) and Electronic Records; Electronic Signatures Regulation (21CFR Part 11).

#### **4.5.5 Battelle Software Development**

The software used in this study in accordance with the Neural Bridge Software Development Plan (SDP), Document D8208-007 which is derived from the guidance provided by the ANSI/AAMI/IEC 62304:2006 *Medical device software – Software life cycle processes* standard. In addition, Battelle follows the FDA guidelines outlined in the *Guidance for the Content of Premarket Submissions for Software Contained in Medical Devices* (issued on May 11, 2005).

## **5. Monitoring Plan**

### **5.1 Plan Description**

The data management for this study will maintain a level of data integrity and confidentiality that will provide optimum adherence to all 21 CFR regulations, while providing a standardized method of data collection and recording to enable the investigators, sponsors and regulatory agencies to accurately reconstruct the events of a study, confirm protocol compliance, and produce data that is accurate and appropriate in demonstrating study results.

Study coordinators at the Ohio State University will perform primary data collection based on source documented hospital chart reviews. Paper case report forms (CRFs) will be used to collect study data. Study coordinators will complete all appropriate sections of the CRFs. The study sponsor/PI will review the information documented in the CRFs and verify the information recorded is consistent with medical records and other source documents. Study staff will rectify errors or incomplete entries. Final CRFs will be reviewed and signed by the principal investigator and/or trained study personnel.

A data and safety monitoring committee (DSMC) will be appointed by the principal investigator to evaluate the accumulating data in this trial (21 CFR 812.46). Members of the clinical trial DSMC, who will have pertinent expertise in their medical and/or scientific field, may be chosen from neurosurgery, neurology, physical medicine and rehabilitation, and neuropsychology. The DSMC can advise the principal investigator and make recommendations on the continuing safety of enrolled trial participants, as well as the continuing validity and scientific merit of the trial.

### **Regulations and Ethical Conduct of the Study**

The study will be conducted according to the clinical investigational plan, and the laws and regulations of the United States, parts, 50, 54, 56 and 812 of the US FDA CFR.

## **PART III – Other Study Information**

### **1. Manufacturing Information**

Refer to documentation on file with FDA by Blackrock. For information on the specific devices to be used in this study, a right of reference letter written by Blackrock, granting permission for the FDA to access such documents will be provided.

#### **6. Device Sales Information**

This study is an investigator/sponsor initiated study utilizing commercially available devices for an unapproved indication. Study participants will not be charged for the device during the study,

and participants will not be paid to participate in the study. The conduct of this study does not involve the sale or commercialization of the therapeutic use of the devices.

## **7. Device Labeling**

**Caution: Investigational device. Limited by Federal law to investigational use only.**

Blackrock Microsystems Neuroport device is a commercially available device being used outside its FDA-approved indications for use (it is being used greater than 30 days). The array used in the Neuroport system has been successfully used in study participants well beyond 30 days, as for example, 1000 days in the Braingate study (Simeral et al, 2011). This investigational system in conjunction with the Battelle Neuromuscular Stimulator or its package will be labeled with the following information: the name and place of business of the manufacturer, packer, or distributor (in accordance with 801.1), the quantity of contents, if appropriate, and the following statement: **"CAUTION--Investigational device. Limited by Federal (or United States) law to investigational use."** In addition, the label will describe all relevant contraindications, hazards, adverse effects, interfering substances or devices, warnings, and precautions. The labeling of the device will not represent that the device is safe or effective for the purposes for which it is being investigated.

These devices will be treated as investigational-use devices since they are being used outside of approved indications and labeling. Information on each device used in the study will be documented, and device accountability for each device used will be maintained. Only approved investigators will implant devices in participants participating in this study.

